8.2.4.2 Adverse Event Collection, Recording, and Reporting

The safety reporting period is defined as the time from the first dose of study drug through 28 days after the last dose of sapanisertib.

Collection and reporting of AE information will begin at the time the patient signs informed consent and continue until any of the following occurs:

- 1. Screen failure
- 2. End of safety reporting period (28 days after the last dose of sapanisertib)
 - a. All AEs and SAEs, regardless of causality, will be collected from the first dose of study drug through 28 days after the last dose of sapanisertib
 - b. Following the safety reporting period, only related SAEs will be collected
- 3. Initiation of a new anticancer treatment.

Recording of AEs: Events that occur after the patient signs the informed consent but prior to initiation of study drug, unless due to a protocol-mandated procedure, will be recorded on the Medical History eCRF. If the event is related to a protocol-mandated procedure, it will be recorded on the AE eCRF. For any patient who subsequently meets eligibility criteria and proceeds to treatment, any event occurring during screening must be documented on the medical history eCRF and in the patient's clinical record. All AEs that occur after the first dose of any study drug treatment must also be documented on the AE eCRF and in the patient's clinical record.

8.2.5 Serious Adverse Event Reporting

All SAEs regardless of attribution, other reportable information, and follow-up information must be reported within 24 hours of learning of the event during the safety reporting period (Section 8.2.4.2), according to the procedures below by completing the SAE form and either emailing or faxing the form to the SAE Reporting Contact below. Following the safety reporting period, only SAEs considered to be treatment-related will be reported. It is important that the investigator provide an assessment of causality (relationship) of the SAE to study drug at the time of the initial report. Calithera Biosciences (or designee) will process and evaluate all SAEs as soon as the reports are received. The medical monitor should also be contacted for any fatal or life-threatening SAE that is considered related to study drug.

Calithera (or designee) is responsible for reporting relevant SAEs to the appropriate regulatory authorities and participating investigators, in accordance with FDA regulations 21 Code of Federal Regulations (CFR) 312.32, International Council for Harmonisation of Technical Requirements for Pharmaceuticals for Human Use (ICH) Guidelines, European Clinical Trials Directive (Directive 2001/20/EC), and/or local regulatory requirements and monitoring the safety profile of the study drug. To meet this requirement, Calithera (or designee) may request additional information from the study sites including, but not limited to, hospitalization records. Any requests for such information should be addressed in a timely manner. Additionally, any SAE considered by an investigator to be related to the study drug treatment that is brought to the attention of the investigator at any time outside of the time period specified for SAE reporting must be reported immediately using the SAE Report Contact form and submitted to the following:

SAE Reporting Details (to be used for submitting the SAE forms):

Reporting of SAEs by the investigator to the IRB or IEC will be done in accordance with the standard operation procedures and policies of the IRB/IEC. Adequate documentation must be maintained showing that the IRB/IEC was properly notified. In accordance with the European Commission Clinical Trials Directive (2001/20/EC), the Sponsor or its designee will notify the relevant ethics committees in concerned member states of applicable

suspected unexpected serious adverse reactions (SUSARs) as individual notifications or through periodic line listings.

8.2.6 Follow-Up of Serious and Nonserious Adverse Events and Other Reportable Information

The investigator must follow-up on all serious and nonserious AEs related to study drugs and other reportable information until the events have subsided, returned to baseline, the patient has initiated another anticancer treatment, or in case of permanent impairment, until the condition stabilizes.

AEs that remain unresolved at the conclusion of the study may continue to be monitored if warranted based on clinical assessment by the investigator and medical monitor.

For AE follow-up, a patient should be contacted by phone and, as appropriate, sent written requests for follow-up information if the patient does not come to the clinic for visits as specified in the schedule of activities (Appendix 1) or as requested by the investigator.

8.2.7 Pregnancy and Pregnancy Reporting Procedure

Patients who become pregnant on study will be required to immediately discontinue study treatment. A pregnancy is not considered to be an AE or SAE; however, any female patient or female partner of a male study patient who becomes pregnant during study participation or within 28 days of last dosing must be reported to the Sponsor using the Pregnancy Report Form within the same timelines as an SAE.

The site will contact the patient at least monthly and document the patient or patient partner's status until the pregnancy has been completed or terminated. A pregnancy will be followed through to outcome. The outcome of the pregnancy will be reported to the Sponsor immediately and within 24 hours if the outcome is a serious adverse experience (eg, death, abortion, congenital anomaly, or other disabling or life-threatening complication to the mother or newborn). The study investigator will make every effort to obtain permission to follow the outcome of the pregnancy and report the condition of the fetus or newborn to the Sponsor. If a male patient impregnates his female partner, the study personnel at the site must be informed immediately and the pregnancy reported to the Sponsor and followed as described above.

AEs and SAEs that occur during pregnancy will be assessed and processed according to the AE or SAE processes using the appropriate AE or SAE forms.

8.3 Clinical Laboratory Safety Tests

Laboratory evaluations (hematology, serum chemistry, and urinalysis) will be performed according to the schedule of study activities (Appendix 1). The laboratory analytes to be tested are summarized in Table 7. All laboratory assessments will be completed by the site local laboratory and results entered in the appropriate eCRF.

Any clinically significant results should be entered as medical history or AEs, depending on the time of the results, in the appropriate eCRF.

Samples will be stored until the specified analyses are completed and then they will be destroyed in accordance with standard laboratory practice and applicable local regulations.

A different clinical laboratory may be used for unscheduled visits or for urgent care. Such laboratory data will not be entered into the study database and these local laboratories will not be included on the Form FDA 1572.

Hematology	Serum Chemistry	Urinalysis	Other
Hematorit Hemoglobin Platelet count Red blood cell count White blood cell count with differential Coagulation PT aPTT INR Fibrinogen	Albumin Alkaline phosphatase (AP) Alanine aminotransferase (ALT) Aspartate aminotransferase (AST) Bilirubin (total and direct)[1] Blood urea nitrogen Calcium (total) Carbon dioxide or bicarbonate Chloride Creatinine Glucose Magnesium	Glucose Blood Ketones Leukocyte esterase Nitrite pH Protein Specific gravity Turbidity & color Urobilinogen Bilirubin Microscopic evaluation (performed at the discretion of the investigator)	For women of childbearing age only: Pregnancy test (serum or urine β-HCG)
	Phosphate Potassium Sodium Total protein Fasting lipid panel (Total cholesterol, triglycerides, LDL cholesterol, HDL cholesterol)		

Table 7: Clinical Laboratory Safety Tests

[1] Direct bilirubin is only required if total bilirubin is above the upper limit of normal.

8.3.1 Fasting Lipid Profile

Prospective monitoring for hyperlipidemia will be managed through fasting lipid testing at the time points specified in the Schedule of Activities (Appendix 1). Patients are required to fast overnight (nothing except water and prescribed medications after midnight or for a minimum of 8 hours) for each of these measurements.

8.3.2 Fasting Serum Glucose Monitoring

Fasting serum glucose will be measured in the study site at the time points specified in the Schedule of Activities (Appendix 1) before administration of sapanisertib, and at other times at the discretion of the investigator. Patients are required to fast overnight (nothing except water and prescribed medications after midnight or for a minimum of 8 hours) for each of

these measurements. In-home glucose monitoring is not required on days when fasting glucose is measured in the study site.

In addition to obtaining fasting glucose levels at the site visits as outlined in the Schedule of Activities (Appendix 1), all patients enrolled in the study will be given a glucometer to monitor their daily fasting blood glucose (FBG) levels at home. The level should be collected daily, predose on dosing days, and at approximately the same time each day. Before checking their blood glucose levels at site visits and at home, patients should fast overnight (nothing except water and/or medications after midnight or for a minimum of 8 hours before the assessment).

On Cycle 1 Day 1, the patient will be provided an in-home glucometer. Patients will be trained on proper use of the glucometer and instructed to collect a daily FBG level every morning (prior to the morning sapanisertib dosing, if applicable), starting on Cycle 1 Day 2. Patients will be instructed to bring the glucometer with them to each study visit so that the data collected can be reviewed and recorded in the source documents. Investigators will be responsible for reviewing the home glucose monitoring logs for hyperglycemia.

The patient will be instructed to contact the site immediately if the value is abnormal (ie, fasting blood glucose $\geq 160 \text{ mg/dL}$ or random blood glucose $\geq 200 \text{ mg/dL}$) for further instructions on the management of their hyperglycemia. Hyperglycemia observed during home glucose monitoring should be confirmed at the study site.

If no irregularities in the FBG level are observed during a minimum of 2 consecutive cycles, then the frequency of in-home FBG testing can be reduced to a minimum frequency of once weekly, depending on the investigator's judgment. Patients will continue to notify the investigator of FBG levels that exceed 160 mg/dL and, if blood glucose levels are not well controlled, or if the patient requires either oral hypoglycemic agents or insulin to control blood glucose levels, then the frequency of in-home testing of FBG levels will be reinstated to daily. See also Section 6.4.1. Patients experiencing hyperglycemia while on study therapy may require more frequent glucose monitoring (eg, BID, TID, QHS), which varies based on severity. Please refer to Table 3 for specific management guidelines.

8.4 Electrocardiograms

Patients should rest in the supine or semi-recumbent position for at least 5 minutes before the 12-lead ECG recording is started. ECG recordings are to be performed as single-tracing evaluations, and must be performed using a standard, high-quality, high-fidelity electrocardiograph machine equipped with computer-based interval measurements. As detailed in Appendix 1, single-tracing ECGs are to be obtained during Screening as well as the following on-treatment time points:

- C1D1: 2 hours (±30 minutes) post dose
- C2D1: 2 hours (±30 minutes) post dose
- C3D1: 4 hours (±30 minutes) post dose

Confidential

When performed, the ECG must be reviewed by a qualified physician (or qualified physician's assistant or nurse practitioner) and any clinically important finding recorded on the appropriate eCRF. ECG results will include heart rate, R-R interval (RR), PR interval, QRS interval, QT interval, and QTcF interval. The corrected QT interval will be corrected for respiratory rate according to the following formula:

Fridericia's formula: $QTcF = QT/RR^{0.33}$

ECGs demonstrating prolonged QTcF > 480 ms, or other clinically significant abnormalities, should be repeated for confirmation. ECGs must be obtained and reviewed at the time points outlined in Appendix 1.

8.5 Vital Signs Measurements and Physical Examinations

Vital sign measurements will include height, weight, resting systolic and diastolic blood pressure, respiratory rate, heart rate, oxygen saturation (SpO₂), and temperature. Height will be measured only at screening.

Complete physical examinations will be performed by a licensed physician (or physician's assistant or nurse practitioner) at screening and the EOT visit. Symptom-directed physical exams can be done on all other visits. System examinations are only required as clinically indicated. The complete physical examination may include dermatologic, cardiac, respiratory, lymphatic, gastrointestinal, musculoskeletal, and neurologic systems, and other systems if clinically indicated by symptoms.

8.6 ECOG Performance Status

ECOG performance status assessments are required to assess patient functional status for study eligibility purposes (during screening within 10 days of randomization) and will be performed throughout the study according to the schedule of activities (Appendix 1). Details of the assessment are shown in Appendix 3.

9 ASSESSMENT OF EFFICACY, SAFETY, PHARMACOKINETIC, AND OTHER ENDPOINTS

Assessments for efficacy and safety will be based on 21-day cycles. Patients will be closely monitored for safety and tolerability while on study treatment up to a defined follow-up period after the last study treatment dose is taken or administered (Appendix 1). All assessments must be performed and documented for each patient.

9.1 Assessment of Efficacy

9.1.1 Assessments for the Primary and Secondary Efficacy Endpoints

The assessment for the primary and secondary efficacy endpoints will include tumor imaging and assessment of survival.

9.1.1.1 Tumor Imaging

The tumor imaging schedule should follow calendar days relative to C1D1 regardless of delays in cycle visits (eg, due to dosing modifications).

Radiographic Tumor Assessments

Radiographic tumor assessments will include chest, abdomen, and pelvis. Diagnostic quality CT with IV contrast or MRI scans with intravenous (IV) contrast will be performed in all patients at screening (within 28 days prior to C1D1) and every 6 weeks (\pm 5 days) from C1D1 onwards. Additional tumor evaluations may occur if clinically indicated.

For patients deemed intolerant to IV CT contrast, a noncontrast CT of the chest may be obtained along with a contrast-enhanced MRI of the abdomen and pelvis. For tumor and tissue resolution, a contract-enhanced MRI of the abdomen and pelvis is preferred over a noncontrast CT of the abdomen and pelvis.

PET-CT: The low dose or attenuation correction CT portion of a combined PET-CT is not acceptable for determining RECIST measurements. However, if the CT performed as part of a PET-CT is of identical diagnostic quality to a diagnostic CT (and includes the use of contrast) then the CT portion of the PET-CT can be used for RECIST measurements and can be used interchangeably with conventional CT in accurately measuring cancer lesions over time. Note, however, that the PET portion of the CT introduces additional data which may bias an investigator if it is not routinely or serially performed.

Baseline brain imaging with contrast enhancement (eg, MRI) is encouraged for all patients at screening. Additionally, patients with a history of brain metastases or symptoms suggestive of CNS metastasis must have contrast-enhanced brain imaging performed at screening. Repeat brain scans will be performed only if the screening brain scan was positive, or as clinically indicated. To optimize the reproducibility and accuracy of the assessment of existing and new tumor burden, the same imaging modality and acquisition protocols used at screening should be employed for all subsequent tumor assessments. Of note, for the

purposes of assessing tumor imaging, the term "investigator" refers to the local investigator and/or the radiologic reviewer located at the site or at an offsite facility.

Imaging should continue to be performed until progressive disease is identified by the investigator, the start of new nonstudy anticancer therapy, withdrawal of consent, or death, whichever occurs first.

Assessment of Tumor Response and Disease Progression

RECIST v1.1 (Appendix 2) will be the primary measure for assessment of tumor response and disease progression for efficacy endpoints.

Patients who discontinue study drug for reasons other than progressive disease or death should be followed by imaging per protocol-defined schedule until progressive disease per RECIST v1.1, death, initiation of a new anticancer therapy, or withdrawal of consent for disease follow-up, whichever occurs first.

9.2 Assessment of Safety

Assessments of safety will include AEs, clinical laboratory tests, ECGs, vital sign measurements, physical examinations, and ECOG status. The reason for permanent treatment discontinuation will also be collected. The procedures for the investigator assessment of AEs are presented in detail in Section 8.2. The procedures for clinical laboratory safety tests, vital sign measurements, ECGs, physical examinations and ECOG status are presented in Section 8.3 through Section 8.6.

9.3 Assessment of Other Endpoints

9.3.1 Assessment of Pharmacokinetics

Sparse blood samples for PK analysis of sapanisertib will be collected at the time points specified in Table 8 and Appendix 1. The dates and exact times of administration of sapanisertib before collection of the blood sample for PK analysis and the dates and exact times of the postdose PK sample collection will be recorded on the eCRF.

Confidentia	1

Study Day	Plasma Sample Collection Timepoints	Sample Amount	
Cycle 1 day 1	Predose (within 1 hour before dosing)	3 mL	ç
Cycle 2 day 1	Predose and 2 hr postdose (±30 min)	3 mL	0
Cycle 3 day 1	4 hr and 6 hr postdose (±30 min)	3 mL	ns
Cycle 4 day 1	1 hr and 3 hr postdose (±30 min)	3 mL	
Cycle 5 day 1	Predose and 2 hr postdose (±30 min)	3 mL 🔊	
Cycle 6 day 1	4 hr and 6 hr postdose (±30 min)	3 mL	

Table 8: Collection Schedule for Pharmacokinetic Assessment

The actual time of PK sample collection must be noted in the source documents. On day 1 of cycles 1, 2, and 5 patients will have their predose sample drawn. Patients must record the time they took their previous dose before day 1 of cycles 2 and 5 and these must be noted in the source documents and eCRFs. Since fasting is required for certain laboratory assessments, sites may offer a light meal or request that patients being a light meal to their visits to consume after laboratory assessments have been completed and before dosing. After completion of the laboratory assessment blood draws, patients will begin consuming the meal approximately 30 minutes before sapanisertib dosing, after which they will take their regularly scheduled doses of sapanisertib. PK blood draws will be taken relative to the study drug dosing regardless of fasting status. In the event of a delay in dosing on scheduled collection days, samples should be collected at a dater study visit. If a patient has not taken sapanisertib for at least 3 consecutive days immediately prior to a visit with PK sampling, samples should be collected at a later study of the patient has taken at least 3 consecutive days of sapanisertib.

Additional information regarding **K** assessments will be provided in the study laboratory manual.

- 9.3.2 Tumor Biopsies
- 9.3.2.1 Archival Tumor Specimen Measurements

Property of F.

Tumor Biopsies 9.3.2.2

Fresh tumor biopsies are not required for study entry.

Analysis of ctDNA 9.3.2.3

10 STATISTICAL METHODS AND SAMPLE SIZE DETERMINATION

10.1 Statistical and Analytical Plans

The primary efficacy endpoint will be the investigator-assessed overall response rate (ORR) as measured by RECIST v1.1. The primary safety endpoint will be measured by the type, incidence, severity, seriousness, and study drug-relatedness of adverse events per CTCAE v5.0. The secondary efficacy endpoints and remaining safety endpoints will also be considered in the overall evaluation.

For Group B (NFE2L2-WT sqNSCLC) a Simon's Two-Stage analysis of ORR will be employed to assist in deciding whether there is sufficient efficacy to continue this Group B to the full planned enrollment. Details can be found in Section 10.5.

10.2 Analysis Populations

The analysis populations for the study are as follows:

10.2.1 Response Evaluable Population

The response-evaluable population includes all patients who receive at least 1 dose of sapanisertib and have measurable disease at baseline and least 1 post-baseline disease assessment. The primary efficacy analysis of ORR will be conducted using response-evaluable population.

10.2.2 Intent-to-Treat (ITT) Population

The ITT population will comprise all randomized patients. Patients in the ITT population will be analyzed for treatment efficacy according to the treatment group to which they are randomized, regardless of post-randomization protocol deviations, including no protocol treatment received.

10.2.3 Safety Population

The safety population includes all patients who receive at least 1 dose of sapanisertib. The safety population will be used for all baseline characteristics, safety analyses, and exposure analysis.

10.3 Efficacy Analyses

10.3.1 Overall Response Rate

Overall Response Rate (ORR) is measured by RECIST v1.1. ORR is defined as the percentage of patients with complete response (CR) or partial response (PR) criteria as assessed by the investigator. Confirmation of response is not required for the ORR, but will be analyzed as supportive data. All tumor evaluations on study are included in the analysis unless they are performed after the patient has received a cancer treatment not allowed by protocol. Descriptive statistics will be used to compare the dose/schedules.

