7.2.1 Prohibited Concomitant Medications and Procedures

Patients are prohibited from receiving the following therapies while in the study treatment phase:

- Other investigational agents or mTOR inhibitors.
- Other anticancer therapies, including but not limited to chemotherapy, immunotherapy, radioimmunotherapy, targeted agents, radiation, or surgery (patients can have palliative radiation or surgery during the study for preexisting lesions).
- Systemic corticosteroids (either intravenous [IV] or oral steroids), unless necessary for treatment of a sapanisertib-related AE (eg, rash). Inhalers and low-dose glucocorticoids for replacement therapy are allowed and in general should not exceed prednisone 10mg or equivalent.
- Anti-epileptic drugs for patients with a history of treated brain metastasis.
- Concomitant administration of any PPI is not permitted during the study. All patients are required to stop taking PPIs at least 7 days before receiving the first dose of study drug. Examples of PPIs include omeprazole, esomeprazole, pantoprazole, lansoprazole, and rabeprazole.
- Acid suppression therapy with histamine H₂ receptor antagonists (H2RA) may be allowed if needed. Sapanisertib should be taken about 2 hours before or 10 hours after H2RA therapy. Examples of histamine H₂ receptor antagonists include ranitidine, famotidine, nizatidine, and cimetidine.
- Administration of neutralizing antacids and calcium preparations is permitted except from 4 hours before until 2 hours after study drug administration. Examples include

aluminum hydroxide (eg, Alternagel, Amphojel), magnesium hydroxide (eg, Milk of Magnesia), and calcium carbonate (eg, Alka-Seltzer, Tums). Anti-gas preparations containing the active ingredients above (ie, aluminum hydroxide, magnesium hydroxide, calcium carbonate) also have antacid properties and should also not be permitted from 4 hours before until 2 hours after study drug administration. However, other anti-gas preparations not containing these active ingredients, for example those with alpha-galactosidase or simethicone as the sole active ingredient, may be taken as needed irrespective of the timing of sapanisertib administration.

- Concomitant administration of strong inhibitors or inducers of CYP3A4 or CYP1A2 must be avoided in this study unless being used to manage an AE. Examples include:

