 - Strong CYP3A4 inhibitors: boceprevir, cobicistat, danoprevir, ritonavir, elvitegravir, indinavir, itraconazole, ketoconazole, lopinavir, paritaprevir, posaconazole, saquinavir, telaprevir, tipranavir, telithromycin, troleandomycin, voriconazole, grapefruit juice
 - Strong CYP3A4 inducers: apalutamide, carbamazepine, enzalutamide, mitotane, phenytoin, rifampin, St. John's wort
 - Strong CYP1A2 inhibitors: ciprofloxacin, enoxacin, fluvoxamine
- Surgical resection of lesions
- Palliative radiation to target lesions is not allowed. Palliative (limited field/stereotactic radiosurgery [SRS]) for isolated, symptomatic non-target lesions and asymptomatic non-target CNS lesions may be performed in the absence of overall progressive disease per RECIST v1.1, provided that the specific plan for palliative XRT is first discussed with and approved by the study medical monitor.
- Live vaccines are not permitted within 28 days prior to first dose and while on study treatment. Examples of live vaccines include, but are not limited to, the following: measles, mumps, rubella, chicken pox, yellow fever, nasal seasonal flu, nasal H1N1 flu, rabies, BCG, and typhoid. Vaccination with SARS-CoV-2 vaccines available via Regular or Emergency Use Authorization granted by the FDA is permitted while on study treatment and should be appropriately documented in the EDC.

During the study, if the use of any concomitant treatment becomes necessary (eg, for treatment of an AE), the treatment must be recorded on the appropriate eCRF, including the reason for treatment, name of the drug, dosage, route, and start and stop dates of administration.

No therapies are prohibited after a patient has permanently discontinued protocol therapy (imaging and survival follow-up periods).

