10.3.2 Duration of Response

For patients achieving a PR or a CR, the DOR will be calculated as the time between the first documentation of a PR or a CR to the first documentation of progressive disease or death, whichever occurs first. For patients achieving first a PR then a CR, the PR date will be the starting date for calculation of the duration of response (DOR). For responders for whom a progressive disease has not been documented yet, the DOR will be censored at the date of the last evaluable radiographic disease assessment prior to the occurrence of any of the following scenarios:

- Patient is alive and progression free at the time of analysis data cutoff.
- Prior to documentation of disease progression the patient receives non-protocol anticancer therapy, or any other treatment that in the opinion of the investigator interferes with assessment of disease per RECIST v1.1.
- Patient misses 2 consecutive scheduled radiographic disease assessments (including missing assessments, insufficient data for the assessments, and an overall response of non-evaluable) followed by RECIST progression at the next assessment.

Conventions regarding censoring for DOR and PFS will be described in the study statistical analysis plan (SAP), as will the planned descriptive statistics comparing the treatment group through Kaplan-Meier and Cox regression statistical procedures.

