10.3.3 Progression Free Survival

PFS is defined as the time from randomization to the first occurrence of disease progression as determined by the investigator using RECIST v1.1 or death from any cause, whichever occurs first. If the disease progression assessment involves more than one date, the earliest date will be used as the event date.

Confidential

For responders for whom progressive disease or death has not been documented at database lock, the duration of PFS will be censored at the date of the last evaluable radiographic disease assessment post-baseline, or lacking a post-baseline assessment using the date of the first study treatment, prior to the occurrence of any of the scenarios described for DOR. Descriptive statistics will be produced comparing the treatment groups through Kaplan-Meier and Cox regression statistical procedures.

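### The scan-exclusion rule for primary ORR is narrower than the DOR and PFS rule, and Section 7.2.1 is unclear about surgery on target lesions

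*Combined protocol and SAP*

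**What the plan says.** **ORR (Section 10.3.1).** All evaluations on study count "unless they are performed after the patient has received a cancer treatment not allowed by protocol". The same section states: "Confirmation of response is not required for the ORR". Confirmed response is supportive only.

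**DOR (Section 10.3.2).** Censoring applies when non-protocol anticancer therapy starts before progression. It also applies after "any other treatment that in the opinion of the investigator interferes with assessment of disease per RECIST v1.1".

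**PFS (Section 10.3.3).** Censoring uses the last evaluable scan "prior to the occurrence of any of the scenarios described for DOR", so the broader rule carries over.

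**What is allowed on treatment (Section 7.2.1).** The bullet on other anticancer therapies adds that "patients can have palliative radiation or surgery during the study for preexisting lesions". Later in the same list of prohibitions stands "Surgical resection of lesions", with no exception. For radiation a specific sentence settles the matter: "Palliative radiation to target lesions is not allowed". After treatment ends, "No therapies are prohibited after a patient has permanently discontinued protocol therapy".

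**Group B rule (Section 10.5).** A dose cohort stops at 0 responses among 9 response-evaluable patients. It rejects the null at 3 or more of 17.

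**The concern.** The primary endpoint has weaker protection against non-drug shrinkage than the two secondary endpoints built on the same scans. Its only safeguard is whether a treatment was allowed, and for surgery the protocol gives two answers. Appendix 2 itself says a protocol must state how new therapy before progression affects best response. Section 10.3.1 answers only for disallowed cancer treatment, and the visible Appendix 2 text does not say how to score a target lesion operated on during the study.

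One scan is enough to make a responder and the cohorts are small, so a single misattributed response carries weight in the Group B stopping rule and in the choice between dose cohorts.

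**Working it through.** **Step 1: the two readings of Section 7.2.1.**

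| Reading | Surgery on a target lesion | Later scans in ORR |
|---|---|---|
| The palliative-surgery allowance governs | Allowed | Counted; a PR is possible |
| The resection ban governs | Resection prohibited | Dropped after resection; effect nil or close to it |

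The bullets can be reconciled if palliative surgery means non-resective surgery only. The protocol does not say so. Even then, a non-resective procedure on a target lesion is allowed and later scans count.

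**Step 2: how much surgery would have to shrink a lesion.** Assume a PR needs a 30% fall in the sum of diameters, with k equal target lesions and the others unchanged. Shrinking one lesion by a fraction s lowers the sum by s/k, so s must be at least 0.30k. That is 30%, 60% or 90% for k = 1, 2 or 3. For k = 4 or 5 it exceeds 100%, so surgery on one lesion cannot suffice alone.

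**Step 3: weight of one response.** 1/9 = 11.1 points of ORR in Group B Stage 1 and 1/17 = 5.9 points at the end of a Group B cohort. In Group A it is 1/15 = 6.7 points in a dose cohort of about 15 and 1/30 = 3.3 points pooled.

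**Step 4: effect on the Group B rule.** The null rate, type I error and power are redacted, so no stated figure can be reproduced. I assume a null of 5%. In a search over 28 optimal-design settings with an alternative of 0.25, only null 5%, type I error 0.05 and power 0.80 returned 0/9 then 2/17.

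With X1 ~ Bin(9, p) and X2 ~ Bin(8, p), P(reject) is the sum over x = 1 to 9 of P(X1 = x) × P(X2 ≥ 3 − x).

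- At p = 0.05, P(reject) = 0.0466, and P(stop early) = 0.95^9 = 0.630.
- At p = 0.25, P(reject) = 0.8122.
- Over assumed nulls of 3% to 10%, P(reject) runs from 0.012 to 0.223.

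Given one certain false responder at p = 0.05:

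- In Stage 1 the cohort always continues, and P(reject) = P(Bin(16, 0.05) ≥ 2) = 1 − 0.95^16 − 16 × 0.05 × 0.95^15 = 1 − 0.44013 − 0.37063 = 0.189.
- In Stage 2, P(reject) = P(X1 = 1) × P(Bin(7, 0.05) ≥ 1) + P(X1 ≥ 2) = 0.2985 × 0.3017 + 0.0712 = 0.161.

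If instead a share q of non-responders is falsely scored PR, the apparent rate is 0.05 + 0.95q:

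| q (assumed) | P(open Stage 2) | P(reject) |
|---|---|---|
| 0 | 0.370 | 0.047 |
| 0.1% | 0.375 | 0.049 |
| 0.5% | 0.398 | 0.058 |
| 1% | 0.424 | 0.071 |
| 2% | 0.475 | 0.101 |
| 5% | 0.603 | 0.212 |

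At plausibly low rates the average effect is near nil. The conditional figures show only what follows once a case has occurred, and any single misread scan would do the same.

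**The case against.** The strongest reply is that the ordinary form of surgical shrinkage is resection, which Section 7.2.1 prohibits outright, so Section 10.3.1 already drops the later scans. Allowing palliative surgery while banning resection is a natural reading. This stands as one of two readings. It does not cover non-resective surgery on a target lesion, and the text does not choose between the two.

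Section 7.2 also opens by permitting concomitant treatment only if the medication is not expected to interfere with evaluating efficacy. It further requires the investigator and medical monitor to agree before a patient who needs a prohibited medication stays on treatment. This narrows the gap. But the condition speaks of medication and looks forward, and neither provision says which scans count.

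A reader might infer three stronger things that the documents do not support.

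- **That the plan as written counts surgical or radiation shrinkage as response.** Radiation to target lesions is expressly barred. For surgery the inference needs the permissive reading, and an investigator might score the lesion as not evaluable anyway.
- **That ORR and DOR contradict each other in practice.** If surgery fell between the week 6 and week 12 scans and week 12 read PR, DOR censored at week 6 would be 6 − 12 = −6 weeks. That requires the same investigator to judge the surgery interfering and still score a PR. Section 10.3.2 also leaves censoring conventions for DOR and PFS to the SAP.
- **That therapy after discontinuation opens a wide gap.** Nothing is prohibited then, so the ORR clause has no clear force. But Sections 5.2.2, 5.2.4.1 and 9.1.1.1 end imaging at new anticancer therapy, and Appendix 2 records best response up to the end of treatment. Only off-schedule scans could be affected.

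**Conclusion.** The point holds as a wording defect in the primary endpoint rule. Section 10.3.1 is narrower than Sections 10.3.2 and 10.3.3, and what it excludes depends on a conflict in Section 7.2.1. The consequence is conditional: a possible unconfirmed PR on the permissive reading, and nil or nearly nil on the restrictive one.

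The size cannot be estimated, because no document gives a rate of surgery on target lesions and the 5% null is an assumption. The case is likely rare. The Group B rule is also softened: Section 10.1 uses it to assist a decision, and Section 10.5 brings in DOR, PFS and safety when the dose is chosen. What remains is that one such response would reverse a 0 of 9 stop, and that preventing it costs almost nothing. Severity: minor.

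**What to change.** 1. **Section 10.3.1.** State that best response uses only assessments made before any non-protocol anticancer therapy, including therapy started after discontinuation. They must also precede any therapeutic surgery, radiotherapy or ablation of a target lesion, and any other treatment that interferes with RECIST assessment, as in the DOR rule. A diagnostic biopsy or aspirate does not count as such a treatment, because Appendix 2 recommends one in some cases before CR is assigned. A CR or PR documented earlier stands. An otherwise response-evaluable patient without one stays in the denominator as a non-responder. This last sentence is needed because Section 10.2.1 makes a patient evaluable on a single post-baseline assessment, which may be the excluded one.
2. **Section 7.2.1.** Amend the parenthetical on palliative treatment to say that surgery on target lesions is not allowed and that palliative surgery is limited to non-resective procedures on non-target lesions, consistent with the resection ban. Leave the radiation rule as it is. Its provision for non-target lesions with medical monitor approval covers radiation only and should not be read across to surgery.

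Amending 7.2.1 alone would bring target-lesion surgery under the existing ORR exclusion. Changing 10.3.1 as well aligns the three endpoints and covers interfering treatment of other kinds.

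**Cost.** A few lines of text, with no added scans or patients. A patient who has therapeutic treatment of a target lesion before responding cannot later count as a responder, so ORR may be very slightly lower.
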